## **9.2.2 Quality of Life Assessments**

### **9.2.2.1 Patient Reported Outcomes**

The EuroQol EQ-5D and EORTC QLQ-C30 questionnaires will be administered by trained site personnel and completed electronically by participants in the following order: EuroQol EQ-5D first, then EORTC QLQ-C30. The questionnaires should be administered prior to dosing at Cycle 1, Cycle 2, Cycle 3, every 2 cycles (ie, every 6 weeks) through Year 1, then every 3 cycles (ie., every 9 weeks) after Year 1 until End of Treatment, and at the 30-day Safety Follow-up Visit.

It is best practice and strongly recommended that electronic patient-reported outcomes (ePROs) are administered to randomized participants prior to drug administration, AE evaluation, and disease status notification. If the participant does not complete the ePROs at a scheduled time point, the MISS\_MODE form must be completed to capture the reason the assessment was not performed.

## **9.3 Adverse Events, Serious Adverse Events and Other Reportable Safety Events**

The definitions of an adverse event (AE) or serious adverse event (SAE), as well as the method of recording, evaluating, and assessing causality of AE and SAE and the procedures for completing and transmitting AE, SAE and other reportable safety event reports can be found in Appendix 4.

Progression of the cancer under study is not considered an adverse event as described in Section 9.3.5 – Disease-Related Events and/or Disease-Related Outcomes Not Qualifying as AEs or SAEs, and Appendix 4.

AE, SAEs, and other reportable safety events will be reported by the participant (or, when appropriate, by a caregiver, surrogate, or the participant's legally authorized representative).

The investigator, who is a qualified physician, and any designees are responsible for detecting, assessing, documenting, and reporting events that meet the definition of an AE or SAE as well as other reportable safety events. Investigators remain responsible for following up AE, SAEs and other reportable safety events for outcome according to Section 9.3.3.

### **9.3.1 Time Period and Frequency for Collecting AE, SAE and Other Reportable Safety Event Information**

All AEs, SAEs, and other reportable safety events that occur after the participant provides documented informed consent, but before treatment allocation/randomization, must be reported by the investigator if the participant is receiving placebo run-in or other run-in treatment, if the event causes the participant to be excluded from the trial, or is the result of a protocol-specified intervention, including, but not limited to washout or discontinuation of usual therapy, diet, or a procedure.

- All AEs from the time of treatment allocation/randomization through 30 days following cessation of study treatment must be reported by the investigator.
- All AEs meeting serious criteria, from the time of treatment allocation/randomization through 90 days following cessation of study treatment, or 30 days following cessation of study treatment if the participant initiates new anticancer therapy, whichever is earlier must be reported by the investigator.
- All pregnancies and exposure during breastfeeding, from the time of treatment allocation/randomization through 120 days following cessation of study treatment, or 30 days following cessation of study treatment if the participant initiates new anticancer therapy must be reported by the investigator.
- Additionally, any SAE brought to the attention of an investigator at any time outside of the time period specified above must be reported immediately to the Sponsor if the event is considered to be drug-related.

Investigators are not obligated to actively seek AE or SAE or other reportable safety events in former study participants. However, if the investigator learns of any SAE, including a death, at any time after a participant has been discharged from the study, and he/she considers the event to be reasonably related to the study treatment or study participation, the investigator must promptly notify the sponsor.

All initial and follow-up AEs, SAEs and other reportable safety events will be recorded and reported to the sponsor or designee within the timeframes as indicated in [Table 9](#).

Table 9 Reporting Time Periods and Timeframes for Adverse Events and Other Reportable Safety Events

Type of Event	Reporting Time Period: Consent to Randomization/ Allocation	Reporting Time Period: Randomization/ Allocation through Protocol-Specified Follow-up Period	Reporting Time Period: After the Protocol Specified Follow-up Period	Timeframe to Report Event and Follow-up Information to SPONSOR:
Non-Serious Adverse Event (NSAE)	Report if: - due to protocol-specified intervention - causes exclusion - participant is receiving placebo run-in or other run-in treatment	Report all	Not required	Per data entry guidelines
Serious Adverse Event (SAE) including Cancer and Overdose	Report if: - due to protocol-specified intervention - causes exclusion - participant is receiving placebo run-in or other run-in treatment	Report all	Report if: - drug/vaccine related. (Follow ongoing to outcome)	Within 24 hours of learning of event
Pregnancy/ Lactation Exposure	Report if: - due to intervention - causes exclusion	Report all	Previously reported – Follow to completion/termination; report outcome	Within 24 hours of learning of event
Event of Clinical Interest (require regulatory reporting)	Report if: - due to intervention - causes exclusion	Report - Potential DILI - Require regulatory reporting	Not required	Within 24 hours of learning of event
Event of Clinical Interest (Do not require regulatory reporting)	Report if: - due to intervention - causes exclusion	Report - non-DILI ECIs and those not requiring regulatory reporting	Not required	Within 5 calendar days of learning of event

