### 2.3 Second Course Phase (Retreatment) for Pembrolizumab (MK-3475)

Trial Period:	Treatment Cycles (3-week Cycles)						EOT	Post-Treatment			Notes: Cycles will be repeated up to 17 infusions or until protocol specific criteria to discontinue treatment is met
Treatment Cycle/Title:	1	2	3	4	5	6 to 17	Discon	Safety FU	FU Visits	Survival FU	
Scheduling Window (Days):	+ 3	± 3	± 3	± 3	± 3	± 3	At time of discon	30D post discon (± 14)	Q6W post discon (± 14)	Q12W (± 14)	
Administrative Procedures											
Eligibility Criteria	X										Participants who either a) attain a CR and discontinue treatment or b) discontinue treatment after 24 months on pembrolizumab for reasons other than disease progression or intolerability may restart trial treatment if they meet the criteria provided in the protocol
Concomitant Medication Review	X	X	X	X	X	X	X	X			Enter new medications started during the trial through the Safety Follow-up Visit.
Pembrolizumab Administration	X	X	X	X	X	X					
Post-study Anti-cancer Therapy Status									X	X	
Survival Status	←----->									X	*Survival FU begins after investigator determined progression or start of next line anticancer treatment. By telephone contact every 12 weeks (84 ± 7 days) until death, withdrawal of consent, becoming lost to follow-up, or the end of the study, whichever occurs first. In addition, upon Sponsor request, participants may be contacted for survival status at any time during the course of the study.
Clinical Procedures/Assessments											
Review Adverse Events	X	X	X	X	X	X	X	X	X		Record all AEs and ECIs occurring within 30 days after last dose of study treatment and SAEs for 90 days after the end of treatment or 30 days after end of treatment if the participant initiates new anticancer therapy (whichever is earlier). Report treatment related SAEs regardless of when they occur.
Full Physical Examination	X						X				
Directed Physical Examination		X	X	X	X	X					

Trial Period:	Treatment Cycles (3-week Cycles)						EOT	Post-Treatment			Notes: Cycles will be repeated up to 17 infusions or until protocol specific criteria to discontinue treatment is met
Treatment Cycle/Title:	1	2	3	4	5	6 to 17	Discon	Safety FU	FU Visits	Survival FU	
Scheduling Window (Days):	+ 3	± 3	± 3	± 3	± 3	± 3	At time of discon	30D post discon (± 14)	Q6W post discon (± 14)	Q12W (± 14)	
Vital Signs	X	X	X	X	X	X	X	X			Prior to dosing assess and record BP, pulse, temperature, and weight.

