Note: Participants who discontinue pembrolizumab after 35 administrations may be eligible for up to 17 administrations (approximately one year) of additional study treatment if they progress after discontinuing study treatment provided they meet additional criteria. Participants who discontinue study treatment before receiving 35 administrations of pembrolizumab for reasons other than PD or intolerability, or who attain a CR and discontinue study treatment, may also be eligible for up to 17 administrations (approximately 12 months of retreatment [Second Course Phase] after experiencing PD). The decision to begin the second course will be at the discretion of the investigator, provided that the participant meets the criteria for treatment, and the study is ongoing (See Section 6.1 and 6.2).

After the End of Treatment (EoT), each study participant will be followed for 30 days for AE and event of clinical interest (ECI) monitoring and 90 days for SAE monitoring. Study participants who discontinue treatment for reasons other than PD will have post-treatment follow-up of disease status until PD, initiating a non-study cancer treatment, withdrawing

consent, or becoming lost to follow-up. All study participants will be followed by telephone contact every 12 weeks ( $84 \pm 7$  days) for survival until death, withdrawal of consent, becoming lost to follow-up, or the end of the study, whichever occurs first. The Sponsor may request survival status to be assessed at additional time points during the course of the study. For example, survival status may be requested prior to the final analysis. All subjects who are in the Survival Follow-Up Phase and not known to have died prior to the request for these additional survival status time points will be contacted at that time.

The trial will be conducted in conformance with Good Clinical Practices (GCPs).

Specific procedures to be performed during the trial, as well as their prescribed times and associated visit windows, are outlined in the Trial SoA - Section 2. Details of each procedure are provided in Section 9 – Study Assessments and Procedures.

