### **6.3.4 Contraception**

Pembrolizumab may have adverse effects on a fetus in utero. Refer to Appendix 5 for approved methods of contraception. For this trial, male participants will be considered to be of non-reproductive potential if they have azoospermia (whether due to having had a vasectomy or due to an underlying medical condition).

Participants should be informed that taking the trial medication may involve unknown risks to the fetus (unborn baby) if pregnancy were to occur during the trial. In order to participate in the trial, participants of childbearing potential must adhere to the contraception requirement (Appendix 5) from the day of trial medication initiation (or 14 days prior to the initiation of trial medication for oral contraception) throughout the trial period up to 120 days after the last dose of trial medication. If there is any question that a participant of childbearing potential will not reliably comply with the requirements for contraception, that participant should not be entered into the trial.

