## 7.2 Dose Modification (Escalation/Titration/Other)

### 7.2.1 Immune-Related Events and Dose Modification (Withhold, Treat, Discontinue)

#### **Dose Modification and Toxicity Management for Immune-related AEs Associated with Pembrolizumab**

AEs associated with pembrolizumab exposure may represent an immune-related response. These irAEs may occur shortly after the first dose or several months after the last dose of pembrolizumab treatment and may affect more than one body system simultaneously. Therefore, early recognition and initiation of treatment is critical to reduce complications. Based on existing clinical study data, most irAEs were reversible and could be managed with interruptions of pembrolizumab, administration of corticosteroids and/or other supportive care. For suspected irAEs, ensure adequate evaluation to confirm etiology or exclude other causes. Additional procedures or tests such as bronchoscopy, endoscopy, skin biopsy may be included as part of the evaluation. Based on the severity of irAEs, withhold or permanently discontinue pembrolizumab and administer corticosteroids.

Dose Modification and Toxicity Management Guidelines for irAEs associated with pembrolizumab monotherapy, coformulations, or IO combinations are provided in [Table 6](#).

**Table 6 Dose Modification and Toxicity Management Guidelines for Immune-related Adverse Events Associated with Pembrolizumab Monotherapy, Coformulations or IO Combinations**

General instructions:				

 
Severe and life-threatening irAEs should be treated with IV corticosteroids followed by oral steroids. Other immunosuppressive treatment should begin if the irAEs are not controlled by corticosteroids.
 
Pembrolizumab monotherapy, coformulations or IO combinations must be permanently discontinued if the irAE does not resolve or the corticosteroid dose is not <math>\leq 10</math> mg/day within 12 weeks of the last treatment.
 
The corticosteroid taper should begin when the irAE is <math>\leq</math> Grade 1 and continue at least 4 weeks.
 
If pembrolizumab monotherapy, coformulations or IO combinations have been withheld, treatment may resume after the irAE decreased to <math>\leq</math> Grade 1 after corticosteroid taper.
 
				
irAEs	Toxicity Grade (CTCAEv4.0)	Action With Pembrolizumab Monotherapy, Coformulations or IO Combinations	Corticosteroid and/or Other Therapies	Monitoring and Follow-up

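### Starting new anticancer therapy ends all-cause SAE and pregnancy collection at day 30 whatever the start date, which conflicts with Section 5.1, the 120-day contraception period and Section 9.3.6

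*Combined protocol and SAP*

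**What the plan says.** **SAEs.** Section 9.3.1 sets the window at 90 days after cessation, "or 30 days following cessation of study treatment if the participant initiates new anticancer therapy, whichever is earlier". The adverse event notes in all three Schedules of Activities (2.1, 2.2, 2.3) repeat the rule. Section 5.1 has no such cut: each participant is "followed for 30 days for AE and event of clinical interest (ECI) monitoring and 90 days for SAE monitoring".

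**Outside the window.** The last bullet of Section 9.3.1, the schedule notes and Table 9 keep drug-related SAEs reportable with no time limit.

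**Pregnancy and breastfeeding exposure.** Section 9.3.1 collects these "through 120 days following cessation of study treatment, or 30 days following cessation of study treatment if the participant initiates new anticancer therapy". Section 6.3.4 requires contraception "throughout the trial period up to 120 days after the last dose of trial medication". Inclusion criterion 14 and exclusion criterion 20 use the same 120 days. None of the three makes an exception for new anticancer therapy. Section 9.3.6 makes any spontaneously reported pregnancy during the trial reportable, including in a male participant's partner. After the follow-up period, the pregnancy row of Table 9 provides only for pregnancies already reported.

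**Scheduled contacts.** Schedules 2.1 and 2.2 mark adverse event review at both follow-up visits and survival contacts. Schedule 2.3 marks it at follow-up visits and leaves the survival cell blank, although its own note asks for SAEs to day 90.

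**The concern.** A cut at new anticancer therapy is normally meant to keep events on the next drug from being counted against the study drug. That purpose calls for a cut at the date the next drug starts. Here the cut is fixed at day 30, so it also removes time when pembrolizumab was the only anticancer drug given. Section 7.2.1 shows why that time matters: "These irAEs may occur shortly after the first dose or several months after the last dose of pembrolizumab treatment".

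The rule is also hard to apply as events occur. An SAE on day 45 is inside the window that day and due to the sponsor within 24 hours. If new therapy starts on day 75, the same event is outside the window in retrospect. Section 10.6.2 does not say whether it is then counted.

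At stake is the completeness of all-cause SAE counts, which feed a secondary safety objective reported by cohort with 95% CIs. The trial is open-label and single-arm, so all-cause collection is the main check on the investigator's judgement of drug-relatedness. For pregnancy, the issue is whether reporting covers the protocol's own 120-day period.

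**Working it through.** The plan gives no figure to reproduce. The check applies the written rule and sets the conflicting texts side by side.

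**SAE window.** Inputs from Section 9.3.1: full window 90 days, reduced window 30 days. Let T be the day new therapy starts, counted from cessation of study treatment.

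- As written, if new therapy starts: end = min(90, 30) = 30 for every T.
- With the cut tied to the start and a 30-day minimum: end = min(90, max(30, T)).
- Gap = second end minus first end. For T from 30 to 90 this is T − 30.

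| New therapy starts | End as written | End if tied to start | Gap (days) |
|---|---|---|---|
| Never | 90 | 90 | 0 |
| Day 10 | 30 | 30 | 0 |
| Day 31 | 30 | 31 | 1 |
| Day 60 | 30 | 60 | 30 |
| Day 75 | 30 | 75 | 45 |
| Day 89 | 30 | 89 | 59 |
| Day 100 | 30 | 90 | 60 |

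The gap is zero for starts by day 30, grows with later starts, and reaches 59 to 60 of 90 days at the end of the window. Read literally, a start after day 90 still pulls the window back to day 30. In the day-75 case, the day-45 SAE precedes the new therapy by 75 − 45 = 30 days and is still excluded.

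**Section 5.1 against Section 9.3.1.** For a participant who starts new therapy, Section 5.1 gives 90 days and Section 9.3.1 gives 30. Both cannot hold.

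**Pregnancy window.** Contraception and no-conception period: 120 days (Sections 6.1, 6.2, 6.3.4). Section 9.3.1 reporting window after new therapy: 30 days. Difference: 120 − 30 = 90 days in which the protocol still requires contraception but Section 9.3.1 no longer asks for reports. Section 9.3.6 has no cut and would cover a spontaneously reported pregnancy in those 90 days, so the two sections conflict. Table 9 does not settle it, because its post-window cell does not address a newly learned pregnancy.

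**Second Course schedule.** Under Section 9.10.4.3, participants with confirmed progression move to survival follow-up by telephone every 12 weeks. In Schedule 2.3 those calls carry no adverse event review. A Second Course participant who stops for progression therefore has no scheduled adverse event contact after the 30-day safety visit, although SAE collection may run to day 90.

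**The case against.** The strongest reply is that little of importance is lost. Drug-related SAEs are reportable at any time, and Schedules 2.1 and 2.2 keep adverse event review at follow-up visits and survival calls, so there is a scheduled route for detecting them. SAEs are summarised as the proportion of participants affected, so lost days change the result only if they contain a participant's first SAE. Pregnancies have Section 9.3.6 behind them.

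Most of this stands, and it rules out several stronger readings that a reader might infer:

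- *Serious immune-related events are lost.* Not supported. Once judged drug-related they are reportable without limit. What leaves the window is SAEs not so judged.
- *The loss falls on participants who move quickly to another therapy.* The arithmetic shows the reverse: none for starts by day 30, most for late starts.
- *Capture differs between the R/M and LA cohorts, or a given share of follow-up is lost.* The documents give no rates or timing of subsequent therapy from which to show either.
- *Pregnancies will go unreported.* Too strong, given Section 9.3.6. The defect is a contradiction plus a gap in Table 9.
- *ECI collection should also run to day 90.* The schedule note does stop it early: "Record all AEs and ECIs occurring within 30 days after last dose of study treatment". But Section 9.3.7 limits ECIs to asymptomatic overdose and one liver-test pattern, and a serious liver event is also an SAE. The remaining gap is mainly non-serious liver abnormalities. No chemistry panel is scheduled after the safety visit, so scheduled detection would need extra blood draws.

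What the reply does not answer is that the drug-related provision is narrower than the window. It depends on the event reaching the investigator and on an attribution that all-cause collection exists to check. Nor does it explain a cut that starts before the new therapy does, or reconcile Section 5.1.

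**Conclusion.** The point holds as a defect in the reporting rule, worth correcting but limited in consequence. For participants who start new anticancer therapy after day 30, SAEs from day 31 to that start that are not judged drug-related fall outside collection. The gap is T − 30 days, up to 59 to 60 of the 90. Section 5.1 contradicts the rule. For pregnancy, 90 of 120 days fall outside Section 9.3.1 once new therapy is started, in conflict with the contraception period and Section 9.3.6. The blank cell in Schedule 2.3 is a smaller omission of the same kind.

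This rests on reading Section 9.3.1 literally. The sponsor may have intended the start date to govern, but no text says so. The effect on reported SAE incidence cannot be sized from the documents; it is likely to be small, and the ORR analysis is untouched.

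**What to change.** 1. In Section 9.3.1 and the three schedule notes, end SAE collection at day 90 or at the start of new anticancer therapy, whichever is earlier, but not before day 30. Keep the unlimited rule for drug-related SAEs. Reconcile Section 5.1 with this text.
2. In Section 9.3.1, run pregnancy and breastfeeding-exposure reporting to day 120 regardless of new therapy, consistent with Sections 6.1, 6.2, 6.3.4 and 9.3.6. Add to Table 9 how a pregnancy first learned of after the window is handled.
3. In Schedule 2.3, mark adverse event review at survival follow-up, as in 2.1 and 2.2.
4. Leave the ECI window as it is.

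The cost is amendment wording and an adverse event question on telephone calls that already take place. Expect a few more SAE and pregnancy reports and a slightly higher reported SAE incidence. No treatment rule changes.

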### **9.3.2 Method of Detecting AE, SAE and Other Reportable Safety Events**

Care will be taken not to introduce bias when detecting AE and/or SAE and other reportable safety events. Open-ended and non-leading verbal questioning of the participant is the preferred method to inquire about AE occurrence.

### **9.3.3 Follow-up of AE, SAE and Other Reportable Safety Event Information**

After the initial AE/SAE report, the investigator is required to proactively follow each participant at subsequent visits/contacts. All AE, SAE and other reportable safety events including pregnancy and exposure during breastfeeding, ECI, Cancer and Overdose will be followed until resolution, stabilization, until the event is otherwise explained, or the participant is lost to follow-up (as defined in Section 8.3). In addition, the investigator will make every attempt to follow all non-serious AEs that occur in randomized participants for outcome. Further information on follow-up procedures is given in Appendix 4.

### **9.3.4 Regulatory Reporting Requirements for SAE**

1. Prompt notification (within 24 hours) by the investigator to the sponsor of SAE is essential so that legal obligations and ethical responsibilities towards the safety of participants and the safety of a study treatment under clinical investigation are met.
2. The sponsor has a legal responsibility to notify both the local regulatory authority and other regulatory agencies about the safety of a study treatment under clinical investigation. All Adverse Events will be reported to regulatory authorities, IRB/IECs and investigators in accordance with all applicable global laws and regulations, i.e., per ICH Topic E6 (R1) Guidelines for Good Clinical Practice.
3. Investigator safety reports must be prepared for suspected unexpected serious adverse reactions (SUSAR) according to local regulatory requirements and sponsor policy and forwarded to investigators as necessary.
4. An investigator who receives an investigator safety report describing a SAE or other specific safety information (eg, summary or listing of SAE) from the sponsor will file it along with the Investigator's Brochure and will notify the IRB/IEC, if appropriate according to local requirements.

